4.2. General Methods

All tabular summaries will present results by treatment. Listings will present data by treatment, country, subject number, and visit (as applicable).

For purposes of all analysis and reporting, days will be numbered relative to the first day of dosing. Day 1 will be defined as the date on which a subject receives the first dose of study drug, as recorded on the eCRF. The day prior to the first dose of study drug is Day -1; there is no Day 0.

Duration variables will be calculated using the general formula (end date - start date) +1.

Appropriate descriptive statistics will be computed and displayed for both continuous and categorical variables. For continuous variables, descriptive statistics will include n (the number of subjects with non-missing data), mean, standard deviation (SD), median, minimum, and maximum values. For categorical parameters, the number and percentage of subjects within each category will be presented. The denominator for percentage will be based on the number of subjects with non-missing data appropriate for summary purposes. Unless otherwise noted, all percentages will be presented to 1 decimal place.

Sort order for data listings will be subject number, visit, and time point where appropriate.

All output will be incorporated into Microsoft Word or Excel files, or Adobe Acrobat PDF files, sorted and labeled according to the International Council for Harmonisation of Technical Requirements for Pharmaceuticals for Human Use (ICH) recommendations, and formatted to the appropriate page size(s).

If the reported value of a clinical laboratory parameter cannot be used in a statistical summary table (eg, a character string is reported for a parameter of the numerical type), a coded value must be appropriately determined and used in the statistical analyses. In general, a value or lower and upper limit of normal (ULN) range such as “<10” or “≤5” will be treated as “10” or “5” respectively, and a value such as “>100” will be treated as “100.” However, the actual values as reported in the database will be presented in data listings. Values that are out of range will be marked as ‘H’ or ‘L.’

Individual patient listings supporting the analyses specified in the SAP will be provided to facilitate the investigation of tabulated values and to allow for the clinical review of all efficacy and safety parameters. Available data at each time point will be presented. Missing data will not be imputed except as noted in [Section 4.6](#).

4.3. Computing Environment

All descriptive statistical analyses will be performed using SAS statistical software Version 9.3 or higher, unless otherwise noted. Medical history and AEs will be coded using the Medical Dictionary for Regulatory Activities (MedDRA) Version 20.0. Concomitant medications will be coded using the World Health Organization (WHO) Drug Dictionary Version March 2016 Format B.

4.4. Baseline Definitions

The last assessments/measurements prior to the first dose of study drug will be used as the baseline reference for all analyses unless stated otherwise.

4.5. Withdrawals, Dropouts, Loss to Follow-up

Subjects who are randomized and withdraw prematurely from the study will not be replaced.

4.6. Missing, Unused, and Spurious Data

Missing data will be handled as outlined below:

- All missing and partial dates for events occurring after randomization or for medications received after randomization will be queried for a value. If no value can be obtained, substitutions will be made as follows:
 - For date of cUTI diagnosis, if the day is missing, day will be defined as “01.” If the month and day are missing, no imputation will be made. For start dates, missing months and days will be defined by “01,” as long as this occurs on or after the first dose of study drug. If the algorithm produces a date prior to the first dose of study drug, the date of the first dose of study drug will be used for the partial date. For stop dates, missing months will be defined as “12” and days will be defined by the last day of the respective month. If the algorithm produces a date after the study discontinuation/completion date, the date of study discontinuation/completion will be used for the partial date. These substitutions will be used in calculations; however, the actual value recorded on the eCRF will be used for all listings.
 - Missing times for AEs will be queried for a value. If no value can be obtained and for all other times for events and assessments occurring after randomization, the time will not be imputed but will remain missing.
- The severity and causality assessment for AEs should not be missing and will be queried for a value. Should there be missing data, AEs with missing severity will be considered severe and AEs with missing relationship to study drug will be considered related to study drug.
- For clinical and microbiological response, missing data will be handled as follows:
 - For the outcome measure of clinical response:
 - Subjects will be defined as an indeterminate if the Investigator cannot determine whether the subject is a clinical cure or failure. Outcome will be defined as missing if the Investigator did not complete the assessment,

or if the subject did not complete the study visit. For the purposes of analysis missing data will be considered indeterminate, and by definition, subjects with an indeterminate response are included in the denominator for analyses in the ITT, micro-ITT and micro-MITT analysis sets, and thus, are considered failures. Subjects with an indeterminate response are excluded from the CE and ME populations.

- For outcome measure of microbiologic response:
 - If no interpretable post-baseline specimen is available, the microbiological response is considered indeterminate. By definition, subjects with an indeterminate response are included in the denominator for analyses in the micro-ITT and micro-MITT populations and thus, are considered failures. Subjects with an indeterminate response are excluded from the ME populations.
- Missing values for other individual data points will remain as missing. Missing values will not be imputed and only observed values will be used in data analyses and presentations.
- Where individual data points are missing, categorical data will be summarized based on reduced denominators (ie, only subjects with available data will be included in the denominators).

4.7. Interim Analyses

A blinded assessment of the proportion of subjects qualifying for the micro-ITT population will be conducted after approximately 800 subjects have been randomized. If the micro-ITT proportion is lower than used in the sample size determination, the sample size may be increased to ensure the study is sufficiently powered. The sample size will not be reduced if the micro-ITT proportion is higher than expected.

A blinded assessment of the overall (aggregated across treatment groups) responder rate (clinical cure and microbiological success) at the TOC visit will be conducted following the completion of approximately 800 subjects. If the overall blinded responder rate is less than the rate used in the sample size calculation for the eravacycline group (71%), the sample size will be increased as needed to ensure 80% power. The sample size will not be decreased if the overall blinded responder rate is greater than the rate used in the sample size calculation. No adjustment to the overall alpha level is required since the sample size adjustment is based on the overall (aggregated across treatment groups) responder rate.

A separate analysis plan will be developed for the interim analysis.

4.8. Visit Windows

Visits will be planned to occur during the visit windows defined in [Table 2](#). If visits occur outside of the defined windows, data will still be collected. All data will be included in by-patient listings. For efficacy and safety analyses, analysis visits will be derived as outlined in [Table 4](#).

Table 4 Derived Analysis Visits for Efficacy and Safety Analyses

Visit	ITT, micro-ITT, and micro-MITT Efficacy Analysis Window¹	CE and ME Efficacy Analysis Window	Safety Analysis Window²
Day 5	N/A	4-6 Days after Randomization	4-6 Days after Randomization
EOI	N/A	Within 1 day of last dose of IV study drug	Within 1 day of last IV dose of study drug
EOT	N/A	Within 1 day of last dose of study drug (IV or PO)	Within 1 day of last dose of study drug (IV or PO)
TOC	N/A	13 – 18 Days after Randomization & ≥ 5 Days after last dose	14-17 Days after Randomization & ≥ 5 Days after last dose
FU	N/A	20-29 Days after Randomization	21-28 Days after Randomization

Key: EOI = End of IV; EOT = End of Treatment; FU = Follow-up; ITT = Intent-to-Treat; MITT = Modified Intent to Treat
 IV = Intravenous; N/A = Not Applicable; PO = Per Oral; TOC = Test of Cure.

1. For ITT, micro-ITT, and micro-MITT analyses, visit windows are nominal.
2. If out of window, the visit will be considered an unscheduled visit.

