Baseline is defined as the value closest to but prior to the start of study drug administration. Analyses will utilize assessments occurring during safety analysis windows (see [Table 2](#)). Thus, if a subject has a visit outside the window, for example, a TOC visit on Day 11, the laboratory assessment will not be summarized with the TOC visit but will be considered an unscheduled assessment. If more than 1 measurement is taken during the visit window, the value taken on the scheduled visit will be utilized or if no scheduled visit was done, the first (earliest) measurement will be used. If more than 1 measurement is taken on the same day, the last measurement on the day will be used. For worst overall post-baseline analyses, all laboratory assessments including those obtained from unscheduled visits will be included.

Several analyses of the laboratory data will be presented. Descriptive statistics (based on SI units) for chemistry, hematology and coagulation values and the change from baseline will be summarized by treatment group at Day 5, EOI, EOT, TOC and FU visits, and for the overall worst value post-baseline (which includes unscheduled visits). Change from baseline will be calculated for each patient at the specified time point as the value at the specified time point minus the baseline value.

Toxicity grade will be determined based on the modified Division of Microbiology and Infectious Diseases (DMID) criteria in [Table 7](#). The DMID Adult Toxicity Table (November 21, 2007) was modified to exclude the clinical component of the toxicity grading. In addition, Grade 0 was added to the table so that shifts from normal could be analyzed. For toxicity grades based on a multiple of the ULN, the normal range from the central laboratory will be applied. For toxicity grades based on fixed values, the grades will be assigned regardless of the normal actual range values from the central laboratory. For example, a hemoglobin value of 10.0 gm/dL will be assigned a grade of 1 toxicity, even if the lower limit of normal from the laboratory was 9.8 gm/dL. Shift tables will be presented to show the number of subjects with a laboratory value with a grade of 0, 1, 2, 3 or 4 at baseline versus the worst post-baseline value.

Table 7 Modified Division of Microbiology and Infectious Diseases Adult Toxicity Criteria (November, 2007)

Hematology					
	Grade 0	Grade 1	Grade 2	Grade 3	Grade 4
Hemoglobin (gm/dL)	>10.5	9.5-10.5	8.0-9.4	6.5-7.9	<6.5

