Activated Partial Thromboplastin (APPT)	<1.01×ULN	1.01-1.66×ULN	1.67-2.33×ULN	2.34-3×ULN	>3×ULN
Prothrombin Time (PT)/International Normalized Ratio (INR)	<1.01×ULN	1.01-1.25×ULN	1.26-1.5×ULN	1.51-3.0×ULN	>3×ULN

Key: ULN = Upper Limit of Normal.

Number and percentage of subjects with at least a 2-grade increase from baseline or a post-baseline grade 4 abnormality (based on DMID criteria) will be summarized by treatment arm. Percentages for each lab test will be based on the number of subjects with a post-baseline evaluation of that laboratory test. A table will be provided which gives all laboratory results for a given laboratory test for subjects who have at least one 2-grade increase from baseline or a post-baseline grade 4 abnormality.

The number and percentage (based on the number of subjects with a normal level at baseline) of subjects in each treatment group with an elevated transaminase level ($>3 \times \text{ULN}$, $>5 \times \text{ULN}$, and $>10 \times \text{ULN}$), an elevated bilirubin level ($>1.5 \times \text{ULN}$ and $>2 \times \text{ULN}$) will be presented by study visit. A table of subjects who meet the laboratory criteria for Hy's law will also be provided. The laboratory criteria for Hy's law is defined as ALT or AST $>3 \times \text{ULN}$, ALP $\leq 2.0 \times \text{ULN}$, and total bilirubin $>2 \times \text{ULN}$.

Detailed patient listings of all laboratory data collected during the study will be provided. Laboratory values outside normal limits will be identified in the patient data listings with flags for low (L) and high (H) as will laboratory values that meet the clinically notable (CN) thresholds.

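### The liver-threshold table is laid out by study visit only, so it cannot count ALT, AST or bilirubin peaks found at central-laboratory draws outside the safety windows

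*SAP*

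**What the plan says.** Three rules in the SAP meet here.

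- **Windows (4.8, Table 4, footnote 2).** The safety windows are 4-6 days after randomization for Day 5, within 1 day of the last IV dose for EOI, within 1 day of the last dose for EOT, 14-17 days and at least 5 days off drug for TOC, and 21-28 days for FU. For safety, "If out of window, the visit will be considered an unscheduled visit".
- **Use of laboratory values (5.8.2).** "Analyses will utilize assessments occurring during safety analysis windows". For a TOC visit outside its window, "the laboratory assessment will not be summarized with the TOC visit but will be considered an unscheduled assessment". Such values return in one place: "For worst overall post-baseline analyses, all laboratory assessments including those obtained from unscheduled visits will be included".
- **The liver-threshold table (5.8.2).** The counts of raised transaminases (>3, >5, >10 x ULN) and bilirubin (>1.5, >2 x ULN), among subjects normal at baseline, "will be presented by study visit". No worst-value or any-time row is specified.

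Elsewhere in 5.8.2 the plan does provide for worst values. The descriptive statistics have an overall worst post-baseline row that takes in unscheduled visits, and the DMID shift table sets the grade "at baseline versus the worst post-baseline value".

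**The concern.** Chemistry is scheduled at Screening, EOI, EOT, TOC and FU (SAP Table 2, note 8). A central-laboratory panel drawn at another time is either a visit that slipped or an extra draw, and an extra draw may well have been prompted by an abnormal finding. The threshold table is the output that sets the two arms side by side at the usual hepatic cut-offs, yet it has no cell for these values. If a peak occurs only at such a draw, the subject is not counted and the by-arm figures are too low. The cut-offs of >3 x ULN for ALT or AST and >2 x ULN for bilirubin matter most: the same section uses them to define the laboratory criteria for Hy's law.

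**Working it through.** The plan states no figure on this point, so there is none to reproduce. The check traces the rules, lists the days that they leave uncovered, and asks whether another output supplies the missing counts.

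**1. Path of an off-window value.** Drawn outside every window -> unscheduled (Table 4, footnote 2; 5.8.2) -> admitted only to worst post-baseline analyses -> the threshold table is by visit and has no worst-value row -> not counted there.

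There is a related case inside a window. If several values exist, 5.8.2 takes the one from the scheduled visit, so an extra in-window draw is also passed over. If there was no scheduled visit, it is used: "if no scheduled visit was done, the first (earliest) measurement will be used".

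**2. Days in no safety window.** Assumptions: first dose on the day of randomization (day 0), one dose a day, and within 1 day read as plus or minus 1. Let V be the number of IV days and T the total treatment days. The last IV dose is then on day V - 1 and the last dose on day T - 1. The windows are Day 5 = 4 to 6; EOI = (V - 1) +/- 1; EOT = (T - 1) +/- 1; TOC = 14 to 17 with day - (T - 1) >= 5; FU = 21 to 28.

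| IV days / total days | Days 1-28 in no window | Count | Count without the Day 5 window (no scheduled chemistry) |
|---|---|---|---|
| 5 / 7 | 1-2, 8-13, 18-20 | 11 | 11 |
| 7 / 7 | 1-3, 8-13, 18-20 | 12 | 13 |
| 5 / 10 | 1-2, 7, 11-13, 18-20 | 9 | 10 |
| 10 / 10 | 1-3, 7, 11-13, 18-20 | 10 | 13 |

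The TOC condition excludes no day here: at T = 10 the last dose is on day 9, and 14 - 9 = 5. The uncovered share is 9/28 to 12/28 (32% to 43%), or 10/28 to 13/28 (36% to 46%) without the Day 5 window. These are calendar days, not subjects or events.

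**3. Can DMID grades supply the counts?** From SAP Table 7:

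| Cut-off in the liver table | DMID band | Recoverable? |
|---|---|---|
| ALT/AST >3 x ULN | inside Grade 2 (2.6-5 x) | No |
| ALT/AST >5 x ULN | about Grade 3 and above (from 5.1 x) | Roughly |
| ALT/AST >10 x ULN | Grade 4 (>10 x) | Yes, as a cut-off |
| Bilirubin >1.5 x ULN | about Grade 2 and above (from 1.6 x) | Roughly |
| Bilirubin >2 x ULN | inside Grade 2 (1.6-2.5 x) | No |

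The baselines also differ. DMID Grade 0 runs to 1.25 x ULN for ALT and AST and to 1.1 x ULN for bilirubin, while the liver table requires a normal baseline.

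**4. What is left unsaid.** The Hy's law table is by subject, and the 2-grade-increase table is based on subjects with a post-baseline evaluation of the test. For neither does 5.8.2 say whether unscheduled values enter.

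**5. A cross-reference to correct.** Section 5.8.2 sends the reader to Table 2 for the safety windows, which are in Table 4. Table 2 gives TOC as at least 3 days after the last dose and Table 4 as at least 5. The two must be reconciled.

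**The case against.** The strongest reply is that the signal survives elsewhere. A subject normal at baseline is DMID Grade 0. Any ALT or AST above 3 x ULN is Grade 2 or higher, as is bilirubin from 1.6 x ULN, so such a subject has at least a 2-grade rise. The SAP tabulates those rises and prints all results of the test for those subjects. The shift table and worst-value statistics include the peak, the listings show every value, and Protocol 13.2 requires clinically relevant laboratory deterioration to be recorded as an adverse event. This stands, with two limits: the SAP does not say that the 2-grade table uses all draws, and none of these outputs gives a by-arm count above 3 x or 2 x ULN.

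A second reply is that the safety windows are no error. TOC at 14-17 days and FU at 21-28 days are the protocol's own visit windows. The CE/ME efficacy windows are a day wider at each end (13-18, 20-29), so a Day 13 TOC visit can count for efficacy while its laboratory values are unscheduled. Widening the safety windows would not reach most of the Day 8-13 gap and is unnecessary once a worst-value row exists. This stands in full.

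A third is that a prompted retest may be run locally. Only central values enter the laboratory database (Protocol 11.1.2 and 13.5), so a new row would not recover local results. This also stands and limits what the change can achieve.

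A reader might also cite a subject whose ALT goes from 1.3 to 4.5 x ULN, Grade 1 to Grade 2, who is in neither the threshold table nor the 2-grade table. That follows from the percentage being "based on the number of subjects with a normal level at baseline) of subjects in each treatment group with an elevated transaminase level", not from the windows. The subject would be left out at a perfectly timed visit too, and still appears in the shift table.

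**Conclusion.** The point holds for one table. As specified, the liver-threshold counts cannot include peaks found at central-laboratory draws outside the safety windows, and two of the counts, transaminases above 3 x ULN and bilirubin above 2 x ULN, cannot be recovered from the graded tables. The conclusion rests on reading by study visit as the table's whole layout: the SAP does not forbid an extra row, but it specifies none here and does specify one for other outputs.

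Two stronger inferences are not supported. One is that hepatic signals at such draws vanish from the analysis; they remain in the outputs named above. The other is that the number of out-of-window visits measures the undercount. The documents give no rate of such visits, and a displaced visit is not a missed elevation. The 9 to 12 days of 28 show where the table is blind, not how many subjects are affected. The direction is known (counts can only be too low); the size is not. The primary and secondary efficacy analyses are untouched. This is a modest gap in safety reporting, worth closing because it costs so little.

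**What to change.** In SAP 5.8.2:

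- Present the transaminase and bilirubin threshold counts *by study visit and for the worst post-baseline value, including unscheduled and out-of-window central-laboratory assessments*.
- State that the Hy's law table and the 2-grade-increase table use the same all-assessments rule.
- Optionally, add a separate row for subjects above normal at baseline.
- Point the safety-window reference to Table 4, and reconcile the TOC off-drug interval between Tables 2 and 4.

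Leave the Table 4 safety windows unchanged. The cost is a few lines of SAP text and a few table rows; no new data are needed. Local-laboratory retests would still be missing from the counts.

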5. STUDY ANALYSES

5.1. Subject Disposition

The number and percentage of subjects included in each of the analysis populations (ie, ITT, Safety, MITT, micro-ITT, micro-MITT, CE-Day 5, CE-EOI, CE-EOT, CE-TOC, CE-FU, ME-Day 5, ME-EOI, ME-EOT, ME-TOC, ME-FU) will be summarized by treatment group, geographic region and country. Regions are as follows: European Union (Austria, Bulgaria, Estonia, Hungary, Latvia, Poland, Romania, Slovakia), Non-European Union Europe (Republic of Moldova, Russia, and Ukraine, Georgia), and North America (United States). Tables will summarize the reasons for exclusion from each population and a listing will be provided that indicates each subject's inclusion/exclusion from the analysis population and the reason for exclusion from each analysis population. The number and percentage of subjects enrolled at each site within each country will also be provided by treatment arm and overall.

The number and percentage of subjects completing the study, prematurely discontinuing from study drug, and prematurely withdrawing from the study will be presented for each treatment group for the ITT, micro-ITT, micro-MITT and ME-TOC populations. Reasons for premature discontinuation of study drug and/or premature withdrawal from the study as recorded on the eCRF will be summarized (number and percentage) by treatment group. Percentages of subjects discontinued from study drug and withdrawals from the study will be compared between treatment groups using Fisher's exact test. A listing of all subjects who prematurely discontinued from study drug or prematurely withdrew from the study will be presented, and the primary reason for discontinuation of study drug or withdrawal from the study will be provided.

5.2. Demographics and Baseline Characteristics

Demographic data and baseline characteristics will be presented by treatment group for the ITT, micro-ITT, micro-MITT and ME-TOC populations. A table will present the subject demographics (eg, gender, age, ethnicity and race) and baseline characteristics (height, weight, BMI, and creatinine clearance) collected before the start of study drug. Age, as collected on the eCRF, will be summarized as both a continuous and categorical variable (<65, 65-75 and >75 years). Creatinine Clearance will be summarized as both a continuous and categorical (<15ml/min, 15 - <60ml/min, >=60, >=130ml/min) variable.

